15.1 Source data and subject data protection

Source data will be registered in patient records or on source data sheets or directly in the e-CRF.

Prior to start of data recording from subjects, the investigator will prepare a Source Data Location Agreement to document where the first recording of data is done.

As a minimum requirement, the following data must be source data-verifiable in source documentation other than the e-CRF:

- Subjects informed consent
- Date of informed consent
- List of randomised subjects

A common e-CRF will be constructed and provide the basis for a central database. Data will in the central database be stored in coded form according to the rules of the Danish Data Protection Agency (Datatilsynet) with whom the trial is registered.

In accordance with the Danish Data Protection Agency data processing will be completed by 01.06.2028.

Afterwards data in paper form will be destroyed and electronic data will be transferred and stored at the Danish Data Archives (Statens Arkiver).

[name] will be responsible for data collection and processing.

In addition, [name], [name], [name], [name], [name] and [name] will be involved in data processing.

The investigator will have direct access to source data and documents in case of monitoring, auditing or inspection from health authorities (Lægemiddelstyrelsen, Videnskabsetisk komité, GCP-enhederne).

15.2 Quality control and assurance

The trial will be carried out according to the protocol, ICH-GCP and current law and it will follow the Declaration of Helsinki.

Quality control and assurance will be carried out in accordance with ICH-GCP and standard procedures will be followed including monitoring, auditing or inspection from health authorities (Lægemiddelstyrelsen, Videnskabsetisk komité, GCP-enhederne).

15.3 Monitoring

Regular monitoring visits will be performed according to ICH-GCP. Data will be evaluated for compliance with the protocol and accuracy in relation to source documents. The monitor will verify that the clinical trial is conducted and data are generated, documented and reported in compliance with the protocol, GCP and the applicable regulatory requirements.

The regional GCP units will conduct the monitoring of sites, regulatory compliance, and review of e-CRFs to source documents. The monitoring will be coordinated from the GCP-unit at Bispebjerg University Hospital, Copenhagen, Denmark. It is the responsibility of the Sponsor that the trial is monitored.

15.4 Research Biobank

During the trial blood samples will be stored at -80°C in a research biobank at Nordsjællands Hospital in pseudo anonymized form. After end of trial and unblinding plasma-mirtazapine and plasma-ondansetron will be analyzed in the respective groups and any left-over material in this research biobank will be kept in a biobank for future research if the subjects have consented to this, or be destroyed in case the subjects have not consented to participate in the biobank.

CONFIDENTIAL

15.5 Biobank

A biobank for possible future research will be established at Nordsjællands Hospital.

The biobank will store blood in pseudo anonymized form at -80 °C for possible later analysis of biomarkers. Samples in the biobank will be stored for 10 years provided subjects acceptance; hereafter the material will be destroyed.

Additional analysis will only be performed after approval by the Committee System on Biomedical Research Ethics. All project related data and samples that can be referred directly to an individual subject will be destroyed immediately or by the closure of the trial.

15.6 Financing

The initiative for this trial was taken by the sponsor, investigator and advisors, none of whom have any financial interest in the trial.

Financial support for the conduct of this study has so far been given to sponsor's research account at Nordsjællands Hospital from Regionernes Medicinpulje who supported the trial with 1,685,096 DKK. This will cover the majority of the trial expenses; salaries (VIP and TAP), laboratory costs, transportation costs for trial subjects and investigator, trial medication, IT-equipment and open access publication. Sponsor, investigator and advisors have no financial links to Regionernes Medicinpulje.

Furthermore, The Research Foundation at Nordsjællands Hospital has supported the trial with 75,000 DKK to cover part of VIP salary.

We are currently applying to other funds for further financing.

15.7 Financial compensation to subjects

The trials subjects will be financially compensated for any documented costs caused by their participation in the trial.

15.8 Insurance

Patients will be covered according to current regulations. Trials in the Danish regions are covered by the patient-insurance (Patienterstatningen).

15.9 Ethical Considerations

Irrespective of the outcome of the trial it will provide useful information on treatment of HG.

The result of the trial will thereby provide physicians and patients with new relevant information guiding their choice of treatment. Currently the treatment offered for severe NVP is not profoundly evidence based and it is often not sufficiently effective, thus 27% of this patient population consider ending the pregnancy and 75% do not wish to become pregnant again.

Based on the number of women exposed to mirtazapine and ondansetron in pregnancy we consider both treatments safe to use in early pregnancy.

All three groups will be allowed to use metoclopramide as rescue medication so no subjects are completely excluded from effective treatment.

16. Publication

The trial is investigator-initiated and data are owned by Region Hovedstaden. Both positive, negative and inconclusive study results will be published via www.clinicaltrials.gov and in an international peer-reviewed scientific journal by the investigators of the study group. [name] will draft the first manuscript.

17. References

CONFIDENTIAL

IMP	Investigational Medicinal Product
NVP	Nausea and Vomiting of Pregnancy
MD	Medical Doctor
OD	Once Daily
PUQE	Pregnancy-Unique Quantification of Emesis and Nausea
SAE	Serious Adverse Event
SAR	Serious Adverse Reaction
SmPC	Summary of Product Characteristics
SUSAR	Suspected Unexpected Serious Adverse Reaction

1. Protocol Synopsis / Summary

Title of trial:

Validating the Effect of Ondansetron and Mirtazapine In Treating Hyperemesis Gravidarum (VOMIT). A double-blind randomized placebo-controlled multicentre trial.

Objectives:

The primary objective is to compare the efficacy of mirtazapine versus placebo on nausea and vomiting in patients with hyperemesis gravidarum.

The secondary objective is to compare the efficacy of ondansetron versus placebo and mirtazapine versus ondansetron on nausea and vomiting in patients with hyperemesis gravidarum.

Trial design:

A double-blind randomized placebo-controlled multi-centre trial. The subjects will be randomised 1:1:1 to receive treatment with either mirtazapine, ondansetron or placebo. The intervention will last for 14 days.

Trial population:

We will include approximately 180 pregnant women with hyperemesis gravidarum, 60 in each group.

Main inclusion criteria:

- Pregnant with gestational age between 5+0 and 11+6
- Nausea and vomiting without other obvious reason
- PUQE-24 score ≥ 13 OR
PUQE-24 score ≥ 7 AND
 1. weight loss $>5\%$ OR
 2. hospitalization due to nausea and vomiting of pregnancy
- Normal singleton pregnancy

Main exclusion criteria:

- Mola-, multiple- or non-vital pregnancy
- Congenital long QT-syndrome
- Ongoing treatment with antidepressant medication
- Not able to take medicine orally
- Not able to understand spoken and written Danish

Methods:

The trial is dimensioned to find a difference in Pregnancy-Unique Quantification of Emesis and Nausea (PUQE)-24 score of 2 with a power of 80% based on a standard deviation of 3 in change in PUQE-24 score, a type 1 error rate of 2,5% and 25% drop out.

Trial endpoints:

The coprimary endpoints are:

- change in PUQE-24 score from baseline to Day 2 (short term) in the mirtazapine group versus the placebo group.
- change in PUQE-24 score from baseline to day 14(+/-1) (long term) in the mirtazapine group versus the placebo group.

PUQE-score (Pregnancy-Unique Quantification of Emesis and Nausea) is a validated scoring system used to grade the severity of nausea and vomiting of pregnancy. It ranges 3-15.

Secondary endpoints include:

- Change in PUQE-24 score on short and long term in the ondansetron group versus the placebo group.
- Change in PUQE-24 score on short and long term in the mirtazapine group versus the ondansetron group.

CONFIDENTIAL

- Area under the curve for PUQE-24 score day 1-14.
- PUQE well-being score.
- Number of daily vomiting episodes.
- Nausea VAS.
- NVPQOL (health-related quality of life for nausea and vomiting during pregnancy).
- HELP (hyperemesis level prediction).
- EQ-5D (a measure of health-related quality of life).
- 7 days PSQI (Pittsburg Sleep Quality Index)
- Patient satisfaction with treatment VAS.
- Patient consideration of termination of pregnancy.
- Occurrence of treatment failure.
- Use of rescue medication.
- Request for dosage increase.
- Days on sick leave.
- Amount of treatments with i.v.-fluids.
- Days of hospitalization.
- Weight change.
- Request for continuation of trial medication after end of intervention.
- Birth outcome (birth weight, gestational age, APGAR, umbilical cord pH, placenta weight, sex, hospitalizations on neonatal ward during the first month, congenital malformations).

Trial medication:

All trial medication will be provided by Glostrup Apotek in accordance with GMP. The investigational medicinal products (IMPs) will be similar in regard to appearance, smell and taste due to the IMPs being encapsulated in gelatine. Each subject will be given two containers one labelled 'Daytime' and one labelled 'Bedtime' to be administered orally in the morning and before bedtime for 14 days.

In the mirtazapine group, the 'Daytime' medication will contain placebo and the 'Bedtime' medication will contain mirtazapine 15 mg.

In the ondansetron group both the 'Daytime' and the 'Bedtime' medication will contain ondansetron 8 mg.

In the placebo group both the 'Daytime' and the 'Bedtime' medication will contain placebo.

Increase in dosage will be possible on Day 7(+/-1) in case of insufficient effect of medication during the first week.

Trial schedule:

Planned first subject first visit:	January 2019
Planned last subject randomised:	July 2020
Planned last subject last visit:	July 2020
End of trial:	January 2021

2. Flowchart

	Screening Day -2-0	Visit 1 Randomisation Day 0	Online questionnaire Day 1-14	Visit 2 Day 7(+/-1)	Visit 3 Day 14(+/-1)	Day 15-17	Postpartum
Informed Consent	x						
In- and Exclusion criteria	x	x		x	x		
Demography	x						
Medical History	x						
Previous and concomitant medication	x						
Changes in concomitant medication		x		x	x		
Vital signs (Height ¹⁾ , weight, BP and pulse)	x	x		x	x		
Physical examination	x						
Ultrasound	x						
PUQE 24-score	x	x	x	x	x		
Nausea VAS, daily vomiting episodes		x	x	x	x		
Rescue medication			x	x	x		
NVPQOL, HELP, EQ-5D, PSQI		x		x	x		
Patient consideration of termination of pregnancy		x		x	x		
Patient satisfaction with treatment VAS				x	x		
Sick leave				x	x		
Hospitalization				x	x		
I.v. fluids				x	x		
Dosage increase				x			
Continuation of trial medication					x		
Side effects, adverse events			x	x	x	x	
Blood samples	x	x		x	x		
Urine sample	x						
ECG	x			x	x		
Randomisation		x					
Dispense of trial medication		x		x			
Drug accountability				x	x		
Birth Outcome							x

1) Height only at screening

3. Background

Refer to the Clinical Trial Protocol 3. **Background/Rationale**.

4. Hypothesis

The hypothesis is that both mirtazapine and ondansetron reduce nausea and vomiting more than placebo in patients with hyperemesis gravidarum.

5. Objectives

5.1 Primary objective

The primary objective is to compare the efficacy of mirtazapine versus placebo on nausea and vomiting in patients with HG.

5.2 Secondary objectives

The secondary objective is to compare the efficacy of ondansetron versus placebo and of mirtazapine versus ondansetron on nausea and vomiting in patients with hyperemesis gravidarum.

6. Study Methods

6.1 Trial Design

A double-blinded randomized placebo-controlled multi-centre trial.

180 subjects will be randomised 1:1:1 to receive treatment with either

- a) Mirtazapine oral tablet 15 mg at bedtime and placebo oral tablet morning,
- b) Ondansetron oral tablet 8 mg morning and ondansetron oral tablet 8 mg at bedtime, or
- c) Placebo oral tablet morning and at bedtime.

The trial subjects will receive treatment for 14 days.

[figure not shown]
A dosage increase will be optional on Day 7(+/-1). If desired the subject will then receive treatment with either

- a) Mirtazapine oral tablet 30 mg at bedtime and placebo oral tablet morning, noon and late afternoon
- b) Ondansetron oral tablet 8 mg morning, noon, late afternoon and at bedtime
- c) Placebo oral tablet morning, noon, late afternoon and at bedtime

Data for the primary endpoint PUQE-24 score will be collected by the subjects completing online questionnaires related to their daily symptoms.

CONFIDENTIAL

Figure 1 – Trial Design

6.2 Randomization

Subjects will be randomised in a 1:1:1 ratio and stratified by site. Randomisation will be performed using REDCap to create a numbered randomisation list. After identification of an eligible patient, the subject will be assigned a randomisation number. The randomisation list will not be accessible to trial personnel involved in the conduct of the trial during the intervention. A printed version of the randomisation list will be kept by a third party to ensure the possibility of unblinding in case REDCap unexpectedly becomes inaccessible.

6.3 Blinding

A double-blind set-up will be used. Mirtazapine, ondansetron and the matching placebo will be similar in appearance and will be packaged identically to maintain the treatment blind. Neither the sponsor, the subject, nor the investigational site staff will know which treatment the subject is receiving.

In case a subject desires to continue the IMP after the intervention, the randomization code for that particular subject can be broken. Thus, for unblinded subjects data collected after unblinding (AEs 0-5 days after the intervention and birth outcome) will not be blinded for the subjects or the clinicians, but the statistician will remain blinded.

Furthermore, the randomisation code for a particular subject can be broken during the intervention in a medical emergency or if knowledge of the IMP is necessary for the optimal treatment of the subject. Whenever a randomisation code is broken, the person breaking the randomisation code must record the time, date and reason as well as his/her initials in the source documents. The sponsor and investigator must be notified immediately after randomisation code break if this happens because of an emergency during the intervention. No matter the reason for unblinding the subject must be discontinued from the trial (birth outcome will still be collected).

CONFIDENTIAL

6.4 Sample size

The trial is dimensioned to find a difference of 2 in PUQE-24 score change from baseline to Day 2 (short term) and/or from baseline to Day 14(+/-1)(long term) between the mirtazapine group and the placebo group with 80% power based on a standard deviation (SD) of change of PUQE-24 score of 3, a type 1 error rate of 2,5% and 25% drop-out. The reason for the 2,5% type 1 error rate is that we want to test 2 hypotheses; effect of mirtazapine versus placebo short and long term on HG.

Thus, we will have to include 57 subjects in each of the 3 groups, which we round up to 60 subjects, equivalent of 180 subjects all together.

A SD of 3 is a conservative estimate based on the placebo-controlled trial with doxylamine-pyridoxine(1,2).

6.5 Framework

Two-sided equality test with the null hypothesis is that the expected difference of the effects of mirtazapine and placebo is zero.

6.6 Interim analysis

There are no planned interim analyses.

6.7 Early termination of the trial

The Sponsor reserves the right to terminate the trial under the following conditions:

- Safety concerns
- If an interim statistical analysis shows that the trial has no scientific value or too low power

If the trial is prematurely terminated or suspended, the investigator should promptly inform the subjects and ensure appropriate therapy and follow-up. Furthermore, the investigator and/or sponsor should promptly inform the pertinent ethics committee and regulatory authorities.

6.8 Timing of final analysis

Final analysis of all endpoints will be performed after the last patient has finished the intervention. All endpoints except birth outcome will be analysed shortly after the last subject has finished the intervention. Analysis of birth outcome will be performed one month after the last patient has given birth. This will allow for registration of possible hospitalization of the new-born.

6.9 Timing of outcome assessments

Baseline characteristics will be assessed on Day 0.

PUQE-24 score, daily vomiting episodes, nausea VAS, administration of IMP and rescue medication and possible side effects will be registered daily by subjects via online questionnaires.

NVPQOL, HELP, EQ-5D, PSQI, patient satisfaction with treatment, patient consideration of termination of pregnancy, number of days on sick leave, amount of treatments with i.v.-fluids, number of days of hospitalisations and weight change will be registered via online questionnaires at Visit 1, 2 and 3.

Request for continuation of trial medication will be registered via online questionnaire at Visit 3.

The visits on Day 7(Visit 2) and Day 14(Visit 3) can be scheduled for day 6-8 and day 13-15 respectively.

Possible treatment failure will be registered when it occurs.

Birth outcome will be registered one month after delivery.

7. Statistical Principles

CONFIDENTIAL

7.1 Confidence intervals and P values

We aim for a p-value of 0.025 for each of the two primary outcomes. This will give a total type 1 error rate of 5% for the hypothesis.

Results will be reported with 95% confidence intervals.

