5.3 Primary endpoints

The coprimary endpoints are:

- Change in PUQE-24 score from baseline to Day 2 (short term) in the mirtazapine group versus the placebo group.
- Change in PUQE-24 score from baseline to Day 14(+/-1) (long term) in the mirtazapine group versus the placebo group.

The change in PUQE-24 score is calculated as baseline score minus Day 2 score and baseline score minus Day 14(+/-1) score, respectively. Baseline values will be recorded at randomisation.

The null hypothesis will be rejected if we find a difference of 2 or more on either short or long term or both.

PUQE-score (Pregnancy-Unique Quantification of Emesis and Nausea) is a validated scoring system used to grade the severity of NVP. PUQE-24 consists of three elements:

- 1) number of hours with nausea within the last 24 hours (from none at all to more than 6 hours),
- 2) number of vomiting episodes in the last 24 hours (from 0 to >6 times), and
- 3) number of retching episodes without vomiting within the last 24 hours (from 0 to >6 times).

Each element gives a sub-score of 1 to 5 points and the total score is calculated by adding the three sub-scores giving a total score ranging from 3 to 15.

The condition is graded as mild if the score is 3-6, moderate with a score of 7-12 and severe if the score is 13-15(3). See Appendix 1.

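### The fixed 0.025 threshold for each primary endpoint is valid, but a Holm step-down would raise the power to claim the second endpoint at the same 5% familywise error

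*SAP*

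**What the plan says.** SAP 7.1 sets the threshold: "We aim for a p-value of 0.025 for each of the two primary outcomes". It gives the purpose in the next sentence: "This will give a total type 1 error rate of 5% for the hypothesis". It then says that results will carry 95% confidence intervals.

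SAP 6.4 explains the split: "The reason for the 2,5% type 1 error rate is that we want to test 2 hypotheses", namely the short-term (Day 2) and long-term (Day 14) effects of mirtazapine against placebo. Protocol 8.3 says the same. The test is two-sided (SAP 6.5): "Two-sided equality test with the null hypothesis is that the expected difference of the effects of mirtazapine and placebo is zero".

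Protocol 5.3 and SAP 9.1 allow a claim "on either short or long term or both". The same sentence ties rejection to an observed difference of at least 2 points. Neither document contains a step-down, a hierarchy or any reuse of alpha after one endpoint is rejected.

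**The concern.** Under the fixed split each endpoint must reach 0.025 whatever the other shows. Once one endpoint has been rejected, part of the 5% that the plan allows is left unused.

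Suppose Day 2 gives p = 0.01 and Day 14 gives p = 0.03. The rule in SAP 7.1 permits only the Day 2 claim. Holm permits both, at the same familywise error. What is at stake is the second of the two hypotheses. In practice this may be Day 14, because Protocol 6.2 expects drop-out and missing data to weigh most at the end of treatment.

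**Working it through.** **Inputs.** All come from SAP 6.4. The target effect is given as "The trial is dimensioned to find a difference of 2 in PUQE-24 score change". The planning power and spread are given as "with 80% power based on a standard deviation (SD) of change of PUQE-24 score of 3". Each test is sized at 0.025, and a quarter of the women are expected to be lost. The plan rounds 57 per group up to 60, so 60 × 0.75 = 45 evaluable per arm. The documents give no correlation between the Day 2 and Day 14 changes, so it is assumed over 0 to 0.9.

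**The plan's own figure.** Per arm, n = 2·SD²·(z₀.₉₈₇₅ + z₀.₈₀)² / δ² = 2·9·(2.241 + 0.842)² / 4 = 42.77. Allowing for drop-out, 42.77 / 0.75 = 57.03. The stated 57 reproduces.

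**Error control.** The fixed split spends at most 0.025 + 0.025 = 0.05; with independent tests it spends 1 − 0.975² = 0.0494. Holm compares the smaller p-value with 0.025 and, if that succeeds, the other with 0.05.
- Both nulls true: a false claim needs the smaller p-value to fall below 0.025, so the bound is again 0.05.
- One null true: a false claim needs at least that endpoint's p-value to fall below 0.05, so the bound is 0.05.

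Neither step uses the correlation. Any endpoint with p < 0.025 is rejected under both rules, so Holm loses nothing. In 2 million simulated pairs per scenario the fixed split never rejected an endpoint that Holm did not.

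**Power by hand, correlation 0.** SE = 3·√(2/45) = 0.632, so the mean z is 2/0.632 = 3.16.
- Single-test power: 0.821 at 0.025 and 0.885 at 0.05.
- Fixed split, both endpoints: 0.821² = 0.675.
- Holm, per endpoint: 0.821 + (0.885 − 0.821)·0.821 = 0.874.
- Holm, both endpoints: 0.885² − (0.885 − 0.821)² = 0.78.
- At least one, either rule: 1 − (1 − 0.821)² = 0.968.

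**Power by simulation** (bivariate normal, 45 per arm, true difference 2 on both days; %):

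| Correlation | Per endpoint, fixed | Per endpoint, Holm | Both, fixed | Both, Holm | At least one, either rule |
|---|---|---|---|---|---|
| 0 | 82.2 | 87.4 | 67.6 | 78.0 | 96.8 |
| 0.3 | 82.2 | 86.9 | 69.9 | 79.3 | 94.5 |
| 0.5 | 82.2 | 86.5 | 71.8 | 80.4 | 92.7 |
| 0.7 | 82.2 | 86.0 | 74.1 | 81.8 | 90.3 |
| 0.9 | 82.2 | 85.2 | 77.5 | 83.6 | 86.9 |

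Under the global null the familywise error is the same for both rules, from 4.95% (correlation 0) to 3.6% (correlation 0.9). With one true null and a true difference of 2 on the other day, Holm's false-claim rate is 4.6% to 3.8% over the same range.

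**Sensitivity of the Day 14 gain.** The gain is the probability that Day 14 falls between 0.025 and 0.05 while Day 2 is significant at 0.025. It therefore depends on the Day 2 effect.
- True Day 2 difference of 1, 45 per arm on both days: Day 14 power rises from 82.2% to 83.8, 83.2, 82.8 and 82.4% at correlations 0, 0.3, 0.5 and 0.7, a gain of 1.6 down to 0.2 points.
- True difference of 2 on both days, no loss at Day 2 (60 per arm) and 45 at Day 14: Day 14 power rises from 82.2% to 87.5–88.1% for correlations 0.7 to 0.

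**Interaction with the 2-point rule.** With 45 per arm and SD 3, p-values between 0.025 and 0.05 correspond to observed differences of about 1.26 to 1.44 (t-test). All lie below 2.

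**The case against.** The strongest reply is that nothing here is wrong. The split is valid and pre-specified, the trial is sized on it, and 57 per group reproduces. Under an either-or-both criterion Holm's first step is the same as the fixed split, so the chance of a positive trial is unchanged. Protocol 6.2 presents the Day 2 endpoint mainly as protection against missing Day 14 data, and no objective requires success on both days. All of that stands. A reader might infer that the plan is underpowered for its stated criterion, or that its type 1 error is faulty; the documents support neither.

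A second reply is that the size of the gain rests on favourable assumptions. It needs a full Day 2 effect, yet Protocol 9.2 gives mirtazapine's time to steady state as 3–4 days. This also stands, and it is why the gain has to be quoted with its range.

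A third is that Protocol 5.3 and SAP 9.1 reject on an observed difference of 2 or more. If that rule governed, the p = 0.01 and p = 0.03 example would fail, since p = 0.03 is an observed difference of about 1.40. Holm would then add no claim unless evaluable numbers fell to about 24 per arm or fewer. That is correct, so the two rules must be reconciled for the change to have any effect.

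The last is that a fixed split pairs exactly with 97.5% intervals and Holm does not. This is a real but small cost. SAP 7.1 already pairs 0.025 tests with 95% intervals, so the interval sentence needs attention in any case.

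What these replies do not remove is that the sample-size sections name two separate hypotheses, and that Holm gives the second a better chance without more patients or more error.

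**Conclusion.** The point holds as an optional efficiency gain. SAP 7.1 is a valid Bonferroni rule; Holm never rejects less and keeps the 5% familywise error under any correlation. At 45 evaluable per arm, SD 3, a true difference of 2 on both days and a correlation of 0 to 0.7, power per endpoint gains about 4 to 5 points and power for both about 8 to 10 points. Power for at least one gains exactly zero, and the required sample size does not change.

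These figures rest on a normal approximation with the planning SD and 25% loss at both time points; the correlation is an assumption. It would be tempting to read the 4 to 5 points as a dependable gain for Day 14. The documents do not support that: it falls to about 0.2–1.6 points if the true Day 2 difference is 1. The whole benefit also requires that the p-value rule, and not the observed difference of 2, decides rejection.

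**What to change.** Make three changes before the randomisation code is added to the cleaned dataset, which is the point by which Protocol 13 requires the SAP to be accepted.

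1. In SAP 7.1, replace the fixed threshold with: *The smaller of the two primary p-values is compared with 0.025; if significant, the other is compared with 0.05 (Holm).*
2. For the two primary comparisons, replace the 95% interval sentence with 97.5% intervals. Add a footnote that an endpoint rejected at the second step may have a 97.5% interval that includes zero.
3. State that this p-value rule governs rejection, and reconcile the 2-point sentence in Protocol 5.3 and SAP 9.1 with SAP 6.5 and 7.1.

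The sample-size text in Protocol 8.3 and SAP 6.4 stays as it is. Items 1 and 2 cost a few sentences of SAP wording and the interval footnote; item 3 also touches one sentence of the protocol. No extra patients or data are needed. If the code has already been added, keep the fixed split, which remains valid.

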9.1 Outcome definitions

Primary endpoint:

The coprimary endpoints are:

- Change in PUQE-24 score from baseline to Day 2 (short term)
- Change in PUQE-24 score from baseline to Day 14(+/-1) (long term) in the mirtazapine group versus the placebo group.

The change in PUQE-24 score is calculated as baseline score minus Day 2 score and baseline score minus Day 14(+/-1) score, respectively. Baseline values will be recorded at randomisation.

The null hypothesis will be rejected if we find a difference of 2 or more on either short or long term or both.

PUQE-24 score (Pregnancy-Unique Quantification of Emesis and Nausea) is a validated scoring system used to grade the severity of NVP. PUQE-24 score consists of three elements:

- 1) number of hours with nausea within the last 24 hours (from none at all to more than 6 hours),
- 2) number of vomiting episodes in the last 24 hours (from 0 to >6 times), and
- 3) number of retching episodes without vomiting within the last 24 hours (from 0 to >6 times).

Each element gives a sub-score from 1 to 5 points and the total score is calculated by adding the three sub-scores giving a total score ranging from 3 to 15.

The condition is graded as mild if the score is 3-6, moderate with a score of 7-12 and severe if the score is 13-15(3). See Appendix 1.

Secondary endpoints:

- Change in PUQE-24 score from baseline to Day 2 in the ondansetron group versus the placebo group.
- Change in PUQE-24 score from baseline to Day 14(+/-1) in the ondansetron group versus the placebo group.
- Change in PUQE-24 score from baseline to Day 2 in the mirtazapine group versus the ondansetron group.
- Change in PUQE-24 score from baseline to Day 14(+/-1) in the mirtazapine group versus the ondansetron group.
- Area under the curve for PUQE-24 score during the intervention in the three different groups.
- Change in PUQE well-being score during the intervention in the three different groups.
- Change in daily nausea VAS during the intervention in the three different groups.
- Change in number of daily vomiting episodes during the intervention in the three different groups.
- Change in NVPQOL (health-related quality of life for nausea and vomiting during pregnancy) from baseline to Day 7(+/-1) and baseline to Day 14(+/-1) in the three different groups.
- Change in HELP score (hyperemesis level prediction) from baseline to Day 7(+/-1) and baseline to Day 14(+/-1) in the three different groups.

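### The two primary comparisons are tested at a two-sided 2.5% level but reported with 95% confidence intervals, so the planned intervals do not match the primary tests

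*SAP*

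**What the plan says.** SAP 7.1 (Confidence intervals and P values) has three sentences. The first sets the level for each primary comparison: "We aim for a p-value of 0.025 for each of the two primary outcomes". The second gives the purpose: "This will give a total type 1 error rate of 5% for the hypothesis". The third sets the interval level for everything: "Results will be reported with 95% confidence intervals".

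The 2.5% level is a deliberate split of alpha. SAP 6.4 explains it: "The reason for the 2,5% type 1 error rate is that we want to test 2 hypotheses". SAP 6.5 makes the test two-sided against zero: "Two-sided equality test with the null hypothesis is that the expected difference of the effects of mirtazapine and placebo is zero". Under SAP 9.1, a positive result on either endpoint is enough to reject.

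Neither document provides 97.5%, adjusted or simultaneous intervals anywhere. SAP 9.2 and Protocol section 13 base the comparisons on the mixed-model standard errors and give no confidence level.

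**The concern.** A two-sided test at level α rejects exactly when the (1 − α) interval excludes the null value. The 95% interval therefore belongs to a 5% test, and the 2.5% test belongs to a 97.5% interval. With the levels set as they are, a primary result with a p-value between 0.025 and 0.05 would fail its planned test and yet be printed with an interval that excludes zero.

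What is at stake is the reading of the primary result. Because one positive endpoint out of two suffices, the split of alpha is needed. The estimate and its interval are what a publication usually shows most prominently, and here the interval would be at a level that ignores the split. The SAP does not say which of the two governs, or that they differ.

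**Working it through.** **Inputs.** Difference 2, SD 3, power 80%, type 1 error 2.5% per test, drop-out 25%, 57 per group rounded up to 60 (SAP 6.4). Two-sided test (SAP 6.5). Total type 1 error 5% (SAP 7.1).

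**Assumptions.** The number of completers is 60 × 0.75 = 45 per arm, and a two-sample comparison stands in for the mixed model. The correlation between the Day 2 and Day 14 estimates is not given in the documents, so a range is shown.

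**1. Reproduce the plan's figures.**
- Total error: 0.025 + 0.025 = 0.05, as stated.
- Sample size: n = 2 × SD² × (z₀.₉₈₇₅ + z₀.₈₀)² / 2² = 2 × 9 × (2.241 + 0.842)² / 4 = 42.8 per group. Then 42.8 / 0.75 = 57.0, the stated 57.
- With a two-sided 5% level (or a one-sided 2.5% level), n = 36 and 36 / 0.75 = 48, which does not reproduce 57. The trial was therefore sized for two-sided 2.5% tests.

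**2. Half-widths at the two levels.** SE = 3 × √(2/45) = 0.632.

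| Quantiles | 95% | 97.5% | Ratio |
|---|---|---|---|
| t, 88 df | 1.987 × 0.632 = 1.26 | 2.280 × 0.632 = 1.44 | 1.15 |
| Normal | 1.960 × 0.632 = 1.24 | 2.241 × 0.632 = 1.42 | 1.14 |

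An observed difference between the two half-widths gives a 95% interval that excludes zero and a test that does not reject. The conflict runs one way: p < 0.025 implies p < 0.05, so a rejecting test always comes with a 95% interval that excludes zero.

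**3. How often this would happen, per comparison.** For true difference d, the probability is P(1.960 < |Z| < 2.241) with Z normal, mean d/0.632 and variance 1.

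| True difference | Probability |
|---|---|
| 0 | 2.5% |
| 1 | 9.8% |
| 1.5 | 10.8% |
| 2 | 6.4% |

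With the t distribution on 88 df, the same calculation gives 2.5%, 9.9%, 11.2% and 6.9%.

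**4. Familywise error, by how significance is judged.** Under the null, it is 1 − P(|Z₁| < c and |Z₂| < c) for a bivariate normal with correlation ρ.

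| ρ (assumed) | Planned tests, c = 2.241 | Read from 95% intervals, c = 1.960 |
|---|---|---|
| 0 | 4.9% | 9.75% |
| 0.5 | 4.6% | 9.1% |
| 0.7 | 4.3% | 8.3% |
| 0.9 | 3.6% | 7.0% |

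The middle column describes the plan as written. The right-hand column applies only if someone sets the 0.025 threshold aside and judges by the intervals.

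**The case against.** The strongest reply is that the plan controls error through the p-value. SAP 7.1 sets 0.025 for each primary outcome, and that control holds whatever interval is printed beside the estimate. No section makes an interval the criterion for success. This stands. A reader might infer that 95% intervals cancel the multiplicity control, or that the trial runs at an error rate of 7% to 10%. The documents do not support either reading, as the middle column of the last table shows.

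A reader might also fault the pair of 95% intervals for joint coverage below 95%. The SAP never calls them simultaneous, and each keeps its own 95% coverage, so this is not a broken promise.

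A third reply points to the other rejection rule, in SAP 9.1 and Protocol 5.3: "The null hypothesis will be rejected if we find a difference of 2 or more on either short or long term or both". On the assumed SE, the conflict zone of 1.26 to 1.44 lies wholly below 2. At an observed difference of 2, both intervals exclude zero (0.74 to 3.26 at 95%, 0.56 to 3.44 at 97.5%). So a result in the zone meets neither written rule, and the 95% interval does not turn a failure into a success. That is correct. It also means that the result would look positive on its interval while failing both rules. How the difference-of-2 rule fits with the p-value rule is a separate question, which changing the interval level does not settle.

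Finally, 95% intervals are conventional, and the zone is only 0.18 points wide (1.44 − 1.26). Both are true. Convention does not make the interval match the test, and the chance of landing in the zone is not negligible if mirtazapine has a moderate effect.

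**Conclusion.** The mismatch is real and lies within one short section. The primary tests are two-sided at 2.5%, and the only intervals planned for them are at 95%. The consequence is limited to reporting and interpretation. Type 1 error, power and sample size stay as planned, provided that decisions use p < 0.025.

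The size is a one-way conflict for p-values from 0.025 to 0.05, with a probability of roughly 2.5% to 11% per comparison over true differences from 0 to 2 points. The existence of the conflict rests on no assumption. The band in points and the probabilities rest on SD 3, 45 completers per arm and the two-sample approximation. The planned mixed model uses all randomised subjects and the full longitudinal data, so the actual band will differ somewhat. The figures of 7.0% to 9.75% are conditional on misreading the intervals and on an assumed correlation.

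It should be corrected, because the remedy is simple and the choice of interval level should not be left until results are known.

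**What to change.** Replace the last sentence of SAP 7.1 with:

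> The two primary treatment differences (Day 2 and Day 14) are reported with 97.5% confidence intervals, matching the 2.5% tests; all other results are reported with 95% confidence intervals.

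A 95% interval may be shown as well for the primary differences, if the text names the 97.5% interval as the one that matches the test.

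The cost is one sentence, with no change to the model, the data or the number of subjects. The two primary intervals become about 15% wider (1.44 / 1.26; about 14% with normal quantiles). The change belongs in the SAP before the randomisation code is added to the cleaned dataset, which Protocol section 13 sets as the point by which the SAP must be accepted.
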